6 STUDY DESIGN

This study will utilize a cluster randomized stepped wedge design. Clusters are defined at the level of care teams and qualifying surgical procedures, and have been randomized to one of five different tranches to implement the intervention at staggered intervals (one new cluster each wave, see diagram below).

The primary outcome of the study is a composite of patient reported pain and function at three months post-surgery. This will enable us to determine the effectiveness of a bundled NOHARM Healing after Surgery Guide + clinical decision support for promoting non-pharmacological pain management strategies to patients undergoing qualifying surgeries, which may also ultimately curb overall patient demand for opioid prescriptions in post-acute post-surgical rehab while optimizing functional recovery. Thus, our secondary outcome(s) is opioid use at the 3 month point post-operatively. This will enable us to understand the impact of our EHR-embedded decision support intervention in an era where opioid prescribing is already being constrained.

All patients receiving common, pre-defined procedures within 7 surgical practice areas at 6 Mayo Clinic locations will receive the study intervention if their surgery date coincides with the stepped wedge implementation schedule. Study locations include Mayo Clinic Rochester, Mayo Clinic Florida, and Mayo Clinic Arizona, as well as three Mayo Clinic Health System sites (Mankato, MN; La Crosse, WI; and Eau Claire, WI). Surgical practice areas will include orthopedic surgery, colorectal surgery, gyn surgery, obstetrics, pulmonary/thoracic surgery, liver and kidney transplant, and cardiac surgery. Due to variable combining of post-op unit care areas, practice size, and related considerations we have formed 22 clusters that will be randomized across 5 tranches.

Enrollment in the intervention arm of the trial will extend from March 2021 to approximately August 2023. Participating practices will be enrolled in the study from the point in time the intervention is implemented in their practice and continuing through the end of the study.

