12 STATISTICAL CONSIDERATIONS

12.1 General Design Issues

This study will address the primary objective using a cluster randomized stepped wedge design. Surgical practices, or clusters, will be randomized in 5 tranches to receive the NOHARM intervention; outcomes of patients treated by these teams will be compared by intervention status of the team. The primary statistical hypothesis is that pain and function measures will be lower and higher, respectively, in the patients treated under the intervention conditions, when compared with non-intervention patients in those same practices.

The cluster randomized stepped-wedge design will allow us to stagger the NOHARM implementation while increasing statistical power. The alternative to staggering the implementation would be to implement at all sites at the same time, which is impractical from a resource perspective. The stepped-wedge design allows each site to serve as its own control, reducing the bias due to imbalanced risk factors across clusters. Contamination does pose some threat to the internal validity of stepped wedge designs when, as here, the intervention rolls out sequentially in adjacent clusters. The 22 NOHARM clusters will minimize potential contamination by capitalizing on geographical separations in the built environments used to deliver perioperative care including different buildings in some cases, as well as subspecialty-designated inpatient wards, office suites, etc.

The primary hypothesis is that the NOHARM intervention will reduce patient reported pain and increase patient reported function following designated surgical procedures relative to patients treated under usual care. The primary outcome – a composite of patient reported pain and function – 3 months post-operatively will be assessed using validated patient reported outcomes.

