12.2 Sample Size and Randomization

Using pain data for 6,261 patients with these procedures at six sites, we estimated the intra-cluster correlation coefficient (ICC) for the pain score to be modest $\rho = 0.037$. To assess minimal detectable effects, we simulated a large number of randomizations and estimated the detectable effect for each. Specifically, for $P = 1, \dots, 5000$ permutations, the 22 clusters were randomly assigned to 5 waves. For each permutation, the closed form solution of Harrison et al (2019) was used to estimate $SE(Q)$ (derived from the formula of Hussey, Hughes (2008)) for true effect Q . We used the values $\sigma^2 = 1$ and $\tau^2 = 0.488$ for the within and between variance components so that detectable effects would be in SDs, and assumed ICC would be 0.037. Over the 5,000 permutations, the detectable effect ranged between 0.048SD and 0.055SD.

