12.2.1 Treatment Assignment Procedures

In order to balance cluster characteristics, we applied a constrained randomization procedure. Constrained randomization allows us to balance a larger number of cluster characteristics than is possible through

stratification. Here the key cluster characteristics to be balanced were: site (6 locations), volume (estimated using 2018 data), procedures (3 groups), and number of teams (1-4). Given only 22 sites, it would not be practical to stratify or apply minimization, while constrained randomization allows us to select an allocation of sites to waves from among a set of allocations that has better balance on these factors.

Specifically, we generated 100,000 allocations of the 22 clusters to 5 waves. For each allocation, we then calculated a balance metric B as follows. For each characteristic c listed above, let $X(c)_i$ be the value of c for each cluster $i=1,\dots,22$. For categorical factors X is an indicator, for volume and number of teams X is a number, rescaled to range from 0-1. Let $w=0,\dots,5$ be the baseline ($w=0$) and 5 intervention waves; and for a given allocation, let S_i = the first wave at which cluster i is allocated to intervention. Then we calculate for each allocation the balance metric

$$B = \sum_{w=0,5} (\bar{S}_i - w) \left| \sum_c X(c)_i (S_i \leq w) - \sum_c X(c)_i (S_i > w) \right|$$

After generating 100,000 allocations, we constrained selection to those with values of B in the lowest decile; we then selected one allocation randomly from those 10,000 ‘acceptable’ allocations. This process resulted in a full allocation of all 22 sites to waves 1-5 prior to initial intervention.

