12.5 Data Analyses

Because patients are randomized in clusters, all statistical methods will account for potential correlation of measures within clusters. Such methods include cluster adjusted standard errors for t-tests and χ^2 -tests, and mixed effects models. Patient characteristics will be summarized by intervention status, and tested for difference between intervention groups; any factors which are imbalanced will be accounted for in the main analyses. Factors assessed for balance and potential inclusion in pre-specified analyses are those listed in Section 13.1.1 and all baseline measures listed in 13.1.2.

The primary and secondary outcomes will be compared between intervention groups using mixed effects generalized linear models. Each model will include an indicator for intervention group; a random intercept for cluster; cluster level factors that were used to constrain randomization; calendar time; surgery type; and any patient factors that were imbalanced across groups.

The model details for each outcome are as follows:

1. PROMIS CATs (anxiety (1°), physical function (1°), pain (1°)). These are continuous measures, collected at two time points, pre-operative and 3 months post-operative. To assess the impact of the intervention on these we will estimate three separate models. If Y_{ijt} is the measure at time $t=1,2$ of the i th patient treated by the j th cluster, then we will estimate

$$Y_{ij2} = \beta_0 + \beta_I I_{ij} + \beta_B Y_{ijo} + \beta_T T + \mathbf{B}_X \mathbf{X}_{ij} + \mathbf{B}_Z \mathbf{Z}_j + u_j + e_{ij} \quad (1)$$

where I_{ij} indicates the intervention status, T is calendar time, $u_j \sim N(0, \tau^2)$ is a cluster level random effect, X_{ij} is a vector of patient characteristics, including surgery type, Z_j is a vector of cluster characteristics used for randomization, and e_{ij} is a residual error. By testing $\beta_I = 0$ we can assess whether the intervention is associated with changes in the corresponding measure.

2. NPPC use. This is collected as a binary value for each of 14 modalities, collected at one time point, 3 months post-operative. We will sum these to create a score, and use a model similar to (1) but without a baseline value Y_{ij0} :

$$Y_{ij} = \beta_0 + \beta_I I_{ij} + \beta_T T + \mathbf{B}_X \mathbf{X}_{ij} + \mathbf{B}_Z \mathbf{Z}_j + u_j + e_{ij} \quad (2)$$

Again by testing $\beta_I = 0$ we can assess whether the intervention is associated with changes in the corresponding measure.

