3. Opioid use will be measured using 4 outcomes:

- a. Hospital-based consumption, daily oral morphine equivalents (OMEs). This is a continuous measure for each day of hospitalization; we will assume that this depends in part on the day post surgery, D_{ij} and model

$$Y_{ij} = \beta_0 + \beta_I I_{ij} + \beta_D D_{ij} + \beta_T T + \mathbf{B}_X \mathbf{X}_{ij} + \mathbf{B}_Z \mathbf{Z}_j + u_j + e_{ij} \quad (3)$$

For this model we will consider D_{ij} as first continuous and then as categorical.

- b. Discharge and post-discharge prescriptions, daily oral morphine equivalents (OMEs). For this outcome, we will use a model analogous to (3), where D_{ij} is replaced by number of days post discharge.
- c. Number of post-discharge prescriptions. These are counts for the 3 month period following surgery. The impact of the intervention will be assessed using a model similar to (2) but with a Poisson link function:

$$\ln(E(Y_{ij})) \sim \beta_0 + \beta_I I_{ij} + \beta_T T + \mathbf{B}_X \mathbf{X}_{ij} + \mathbf{B}_Z \mathbf{Z}_j + u_j + e_{ij} \quad (4)$$

$$Y_{ij} \sim \text{Poisson}(\mu)$$

We will assess the distribution first using an empty model, and potentially adopt a zero inflated Poisson, negative binomial, or zero inflated negative binomial according to the corresponding AIC values.

- d. Daily use of opioids; this is binary outcome collected one time, at 3 months post-surgery. To assess the impact of the intervention we will use a model similar to (4) but with a logit link:

$$\text{logit}(Y_{ij}) \sim \beta_0 + \beta_1 I_{ij} + \beta_2 T + \mathbf{B}_X \mathbf{X}_{ij} + \mathbf{B}_Z \mathbf{Z}_j + u_j + e_{ij} \quad (5)$$

For a-d we can again test $\beta_1 = 0$ we can assess whether the intervention is associated with changes in the corresponding measure.

4. Healthcare utilization

- a. Hospitalizations
- b. ER visits
- c. Calls to surgical practice

All three of these are count outcomes, and so we will assess the impact of the intervention using a model similar to (4) above. As with (4), we will compare model specifications using an empty model first to determine the best count family (Poisson, negative binomial, zero inflated or not) using AIC, then apply that in the final model.

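### The planned models and the detectable effect allow only a constant cluster effect; if clusters drift apart over time, standard errors are too small and the detectable effect is understated

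*Combined protocol and SAP*

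**What the plan says.** Section 12.5 defines the random part of every model: "Each model will include an indicator for intervention group; a random intercept for cluster". In equation (1) the cluster effect u_j carries no time index, the residual is at patient level, and "T is calendar time", a single term shared by all clusters. Models (2) to (5) repeat this form; for daily opioid use, for example, "we will use a model similar to (4) but with a logit link". Cluster-adjusted standard errors are mentioned for t-tests and chi-square tests, not for the mixed models.

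Section 12.2 uses the Hussey-Hughes variance with one within-cluster and one between-cluster component and an ICC of 0.037, and reports: "Over the 5,000 permutations, the detectable effect ranged between 0.048SD and 0.055SD". Alpha, power and the analysed number per cluster and period are not given with that figure.

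Section 12.1 gives the logic of the design: "The stepped-wedge design allows each site to serve as its own control". Section 6 gives the time span: "Enrollment in the intervention arm of the trial will extend from March 2021 to approximately August 2023". It also lists 7 practice areas at 6 locations.

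Nowhere do the documents contain a cluster-by-period term, a cluster-specific trend, a decaying correlation, a stated robust variance for the mixed models, a CAC, or a sensitivity analysis that relaxes the constant cluster effect.

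**The concern.** With only u_j, two patients of one cluster are equally correlated whether they had surgery in the same month or two years apart. That is CAC = 1. The calendar-time term removes change common to all clusters, but not change specific to one.

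In a stepped wedge, the intervention contrast is largely a before-and-after comparison within each cluster, so cluster-specific change feeds straight into the estimate. The planned model treats that change as patient noise and divides it by the number of patients. It should be divided by the number of cluster-periods. More patients make the discrepancy worse.

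At stake are the confidence intervals and p-values for both co-primary outcomes, pain interference and physical function, which both come from model (1). The error runs towards false positives. The trial is also sized for a very small effect, so drift too small to notice clinically can matter.

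**Working it through.** **Inputs from the documents.** 22 clusters and 5 tranches (section 6); baseline plus 5 waves, so 6 periods (section 12.2.1); ICC 0.037 and σ² = 1 (section 12.2); 114,000 planned patients (section 1.5).

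**Assumptions.** Equal clusters, waves of 5/4/4/4/5, two-sided 5%, 80% power, and total ICC held fixed while CAC varies.

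**Between-cluster variance.** ICC 0.037 with σ² = 1 implies τ² = 0.037/0.963 = 0.0384. Section 12.2 prints τ² = 0.488, which would mean an ICC of 0.488/1.488 = 0.328. The value implied by the ICC is used here. It gives the milder result once drift is allowed.

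**The plan's figure.** The detectable effect is 2.80 × SE under the random-intercept formula. With m = 265 analysed per cluster-period (35,000/132), SE = 0.0190 and the detectable effect is 0.053 SD. The ends of the stated range, 0.055 and 0.048 SD, correspond to m = 247 and m = 325. With all 114,000 analysed (114,000/132 = 864 per cell) the formula gives 0.030 SD, below the stated range. The figure therefore cannot be reproduced exactly, and m = 265 is a back-calculated size.

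**Adding drift.** Let ω² = τ²(1 − CAC) be the cluster-by-period variance. The true covariance of one cluster's six period means is

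V = τ²·CAC·J + (ω² + σ²/m)·I,

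where J is the all-ones matrix and I the identity. The intercept-only model works with

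V_w = τ_w²·J + ((σ² + ω²)/m)·I.

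The model variance of the intervention effect comes from (X′V_w⁻¹X)⁻¹. Its true variance is the sandwich (X′V_w⁻¹X)⁻¹ X′V_w⁻¹ V V_w⁻¹X (X′V_w⁻¹X)⁻¹. Type I error is 2(1 − Φ(1.96 × model SE / true SE)).

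**By hand at CAC 0.95.** ω² = 0.05 × 0.0384 = 0.00192, an SD of 0.044, which is smaller than the target effect. The within-cluster variance of a period mean is 1/265 + 0.00192 = 0.00569. The model takes it as 1.00192/265 = 0.00378. The ratio of standard errors is about √(0.00569/0.00378) = 1.23. The full matrix calculation gives 1.22, and 2(1 − Φ(1.96/1.225)) = 11%.

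**Results at m = 265.** The model SE stays at 0.0190 throughout.

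| CAC | True SE | True / model SE | Type I error | Detectable effect, drift modelled | Power at 0.053 SD, drift modelled |
|---|---|---|---|---|---|
| 1 | 0.0190 | 1.00 | 5% | 0.053 | 80% |
| 0.99 | 0.0199 | 1.05 | 6% | 0.056 | 76% |
| 0.95 | 0.0232 | 1.22 | 11% | 0.065 | 63% |
| 0.90 | 0.0268 | 1.41 | 17% | 0.075 | 51% |
| 0.80 | 0.0328 | 1.73 | 26% | 0.091 | 37% |

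Simulation with 20,000 replicates gives type I error of 6.2, 10.9, 16.3 and 25.7% for CAC 0.99 to 0.80. Categorical periods and a linear T give the same SE ratios.

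**Sensitivity** (type I error at CAC 0.99 / 0.95 / 0.90 / 0.80):
- ICC 0.02 after covariate adjustment, m = 265: 6 / 8 / 11 / 17%.
- All 114,000 analysed, m = 864: 9 / 23 / 34 / 48%.
- 38,000 analysed with waves of 4/4/4/5/5: 6.3 / 11.5 / 17.5 / 27.1%.

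**The case against.** The strongest reply is that no error has been shown. The documents give no CAC, nothing in them proves that clusters drift, and at CAC 1 the plan is correct. That stands: the finding is conditional, and its size depends on CAC and the analysed number.

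Second, the printed range of 0.048 to 0.055 SD is not shown to be wrong in absolute terms. If all 114,000 patients were analysed, a CAC of 0.95 would give 0.048 SD, and 0.055 SD would stay detectable down to a CAC of about 0.93. This also stands. The understatement is relative to the same inputs. In that scenario, however, the type I error is at its worst (23% at CAC 0.95).

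Third, section 12.2 attributes its range to allocation, not to sample size, and real cluster volumes differ. This is correct. The mapping to 247 to 325 per cell only locates a plausible size.

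Fourth, baseline score, surgery type and patient factors in model (1) can absorb drift caused by measured case mix. They can, which is why the ICC 0.02 case is shown; inflation shrinks but remains.

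Fifth, the shape of drift matters. Smooth linear cluster trends with the same variance give 8, 11 and 17% at CAC 0.95, 0.90 and 0.80, and the proposed model is then conservative (about 3, 2 and 2%). Autoregressive decay gives 17, 26 and 38%, with the proposed model near nominal. Inflation is present in every case.

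Sixth, the wording of section 12.5 does not exclude robust errors for the mixed models. It does not specify them either.

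**Conclusion.** The concern holds as a conditional statement. The analysis models and the detectable effect both assume CAC = 1 without saying so, and any lower value makes the model SE too small and the detectable effect larger on the same inputs. At about 265 analysed per cluster-period and ICC 0.037, type I error is already above 10% at CAC 0.95, and the detectable effect of 0.056 SD at CAC 0.99 lies above the upper end of the stated range.

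These figures rest on equal clusters, independent period shocks, 80% power, and assumed values of CAC and analysed number. If the printed τ² of 0.488 were the true between-cluster variance, the effect of drift would be far larger: with 38,000 analysed and CAC 0.95, the detectable effect is 0.146 SD rather than 0.064 SD. Inflation in the count and logit models was not computed. Because both co-primary tests are affected and the remedy is cheap, this should be changed before analysis.

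**What to change.** Add a random cluster-by-period intercept, v_jk ~ N(0, ω²), to models (1) to (5). Define period k by the steps already set out in section 12.2.1 (baseline plus waves 1 to 5). For the linear models, specify Satterthwaite or Kenward-Roger degrees of freedom.

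Restate the section 12.2 detectable effect for CAC 1.0, 0.95, 0.9 and 0.8, with the alpha, power and analysed cluster-period size behind it. Reconcile τ² = 0.488 with the ICC of 0.037 at the same time, because the discrepancy matters once drift is allowed.

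The cost is SAP wording and one variance component, with no new patients or data. Confidence intervals widen if there is drift, and the stated detectable effect becomes less favourable. If there is none, simulation at 265 per cell shows the mean SE rising about 3% and power at 0.053 SD going from 80% to 78%.

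In 10,000 replicates, REML with both random intercepts kept type I error between 4.1 and 5.4% over CAC 1 to 0.80, at 265 and at 864 per cell. That check covered linear models only and used a fixed 104 degrees of freedom (132 cells − 22 clusters − 5 periods − 1), not the Satterthwaite or Kenward-Roger method itself.

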5. Failure to apprise the IRB of updated patient contact materials or study procedures.

It is possible that some of the patient contact materials, including elements of the decision aid, after visit summaries, and resource materials provided to patients will be updated with alternate and or additional information throughout the course of the study. Failure to apprise the IRB of these modifications and/or to document these updates as potentially important covariates in analysis will be considered a deviation from protocol.

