3. It would be impracticable to formally track clinicians as we are not documenting individual consent nor collecting data from clinicians. Although we could potentially identify the number of clinicians who log into Epic to provide care for discreet surgery patients, this approach would be imprecise.
4. No clinician variables—including clinician ordering or prescribing behaviors—are being assessed. All study outcomes are patient outcomes, as the intervention is intended to guide the patient’s surgical recovery experience.

Risks and Benefits

The risks to clinicians involved in the NOHARM trial are minimal. Clinicians are already motivated to employ clinical guidelines for non-pharmacological pain management, and the NOHARM pilot study may enhance their personal success that effort. Clinicians may find, perhaps at first, that the EHR-based prompts interfere with the rhythms of their workflow, but

great effort has been invested to ensure that the EHR-embedded clinical decision support tools integrate seamlessly into existing workflows. Further, the Mayo Clinic Clinical Practice Committee has endorsed the intervention as an appropriate element for institutional improvement in the management of post-surgical pain. Ongoing care will be taken to minimize the workflow burden while making the EHR prompts an effective tool in promoting institutional adherence to clinical guidelines. Clinicians will always be able to make professional judgments about the appropriateness of engaging patients in specific conversations about pain management throughout the patients' post-surgical recovery. Clinicians may freely disregard EHR-prompts as they deem appropriate in their professional judgment. Clinicians will be amply supported by the study team by way of education and through access to study team members with expertise in non-pharmacological pain management modalities and in the management of complex pain management cases.

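### Every model assumes a constant effect from activation and no planned analysis checks it; if the effect starts weakly, the stepped-wedge estimate will understate it by more than a simple average would

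*Combined protocol and SAP*

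**What the plan says.** Section 12.5 sets one form for all outcomes: "Each model will include an indicator for intervention group; a random intercept for cluster", with the randomization factors, calendar time, surgery type and imbalanced patient factors. In model (1), I_ij "indicates the intervention status, T is calendar time". By testing its single coefficient against zero, "we can assess whether the intervention is associated with changes in the corresponding measure". Models (2) to (5) repeat the structure.

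Section 6 states that "we have formed 22 clusters that will be randomized across 5 tranches". Section 12.2.1 defines a baseline and "5 intervention waves; and for a given allocation", which makes six periods.

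No section contains a time-since-activation term, a wash-in period, a random intervention effect or a sensitivity analysis for a changing effect. The moderators in Section 12.7.1 are procedure, age, sex and race/ethnicity. The subgroup and mediation analyses reuse the same models or address other questions.

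Three places bear on whether the effect could vary after activation:
- Section 8.1 has the guide sent when the surgery order is entered, whereas Section 6 assigns exposure by surgery date.
- Appendix A, on risks to clinicians, says "Clinicians may find, perhaps at first, that the EHR-based prompts interfere with the rhythms of their workflow".
- Section 13.3.4, item 5, treats it as possible that some patient materials "will be updated with alternate and or additional information throughout the course of the study", and refers to such updates as potential covariates without specifying a term.

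**The concern.** Calendar time in the model absorbs secular trend. It does not absorb change with time since a cluster was activated. When the effect depends on time since activation, a stepped-wedge model with one indicator does not return the average effect over the exposed periods. It leans heavily on the first periods after activation and can give the latest ones negative weight.

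At stake is the reading of both co-primary results. A bundle that takes time to bed in would look weaker than it was on average, and one that fades would look stronger. With only the analyses now planned, neither would be visible.

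**Working it through.** **Inputs from the document.** 22 clusters and 5 waves (Section 6); baseline plus five waves (12.2.1); ICC 0.037 and within-variance 1 (12.2); 114,000 patients (1.5).

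**Assumptions.** Waves of 5, 5, 4, 4, 4 (sizes are not given); equal periods; equal volumes, so 114,000 / (22 × 6) = 864 patients per cell; an effect that depends only on periods since activation; covariates left out. Between-cluster variance: 0.037 / 0.963 = 0.0384. Section 12.2 also prints 0.488 for this component, which does not match the ICC but barely changes these results.

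**The plan's own figure.** The Hussey-Hughes formula with these inputs gives SE 0.0106. At two-sided 0.05 and 80% power the detectable effect is 2.80 × 0.0106 = 0.030 SD. The plan states 0.048 to 0.055 SD, which would correspond to about 43,500 down to 33,000 analysed patients. Section 12.2 does not state alpha, power, cluster volumes or analysable numbers, so this mismatch does not show an error. The weights below hardly depend on it: at 288 patients per cell each moves by less than 0.01.

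**Weights.** For cluster i, let D_i hold the 0/1 indicator and the period effects, E_i the five exposure-period indicators, and V = (1/864) × identity + 0.0384 × (matrix of ones). If the true effect in exposure period k is d_k, the expected estimate is the sum of w_k × d_k. Here w is the first row of (Σ D_i' V⁻¹ D_i)⁻¹ (Σ D_i' V⁻¹ E_i).

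| | k=1 | k=2 | k=3 | k=4 | k=5 |
|---|---|---|---|---|---|
| Waves 5,5,4,4,4 | 0.853 | 0.375 | 0.054 | -0.131 | -0.150 |
| Waves 4,4,5,4,5 | 0.853 | 0.363 | 0.035 | -0.117 | -0.135 |
| 5,5,4,4,4, linear time | 0.862 | 0.386 | 0.052 | -0.142 | -0.159 |

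Each row sums to 1. In 500 random sets of unequal volumes (coefficient of variation about 1, waves 4,4,5,4,5), the central 95% of weights ran from -0.16 to -0.06 for period 4 and from -0.22 to -0.07 for period 5.

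**Effect curves.** Exposed cells by period since activation number 22, 18, 14, 10 and 5, 69 in all. These are the patient weights. The full effect is set to 1, and the first row of weights is used.

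| Effect in periods 1 to 5 | Model estimate | Patient-weighted average | Equal-weight average |
|---|---|---|---|
| 0.5, 1, 1, 1, 1 | 0.57 | 0.84 | 0.90 |
| 0.2, 0.4, 0.6, 0.8, 1 | 0.10 | 0.48 | 0.60 |
| 0, 0, 1, 1, 1 | -0.23 | 0.42 | 0.60 |
| 1, 0.8, 0.6, 0.4, 0.2 | 1.10 | 0.72 | 0.60 |

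First row: 1 - 0.5 × 0.853 = 0.57; patient-weighted, (69 - 11) / 69 = 0.84. Third row: 0.054 - 0.131 - 0.150 = -0.23 (-0.22 with waves 4,4,5,4,5).

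**In SD units.** A full effect of 0.055 SD with a half-strength first period would be estimated at about 0.055 × 0.57 = 0.031 SD, below the stated detectable range.

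**Shorter delays.** Section 6 says "Enrollment in the intervention arm of the trial will extend from March 2021 to approximately August 2023", about 30 months, so five equal steps last about 6 months each. With waves 4,4,5,4,5, a linear build-up over 3 months gives 0.79 against a patient-weighted 0.91, and over 6 months 0.57 against 0.83. Both keep the right sign.

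**The case against.** The strongest reply is that the document does not predict a changing effect, and that is correct. The Appendix A remark is hedged, concerns workflow rather than patient outcomes, and goes on to stress the effort put into smooth integration. The statement on materials is conditional. Updates would most naturally fall on calendar dates across all active clusters, so a model in time since activation would not isolate them. Much of the bundle is automated and reaches each new patient, and Section 7.3 lets patients choose modalities in hospital. The hints that remain, the order-triggered guide and possible early friction, point to a short delay.

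A reader might infer from the negative weights that the trial is likely to report no effect or the wrong sign. The documents do not support that. Near-zero estimates need growth over most of the roll-out, and a clear reversal needs at least two whole periods without effect, or convex growth.

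It is also fair that the single-indicator model matches the formula used for power in Section 12.2, so design and analysis agree. That supports keeping it as primary. It does not show that the effect is constant, and nothing else planned would test this.

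**Conclusion.** The gap is real and moderate. The primary estimate is interpretable as planned only if the effect is constant from activation, and the plan offers no check. A half-strength first period would bring the estimate to about 57% of the full effect, against 84% averaged over exposed patients. Growth across the whole roll-out would bring it to about 10% against 48%, and a matching decline would raise it to about 110% against 72%.

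These sizes rest on assumed wave sizes, equal periods and illustrative effect curves, since the document gives no build-up speed. The pattern of weights is stable across the wave splits, time codings and volumes tried. It was computed for the linear models; the count and binary models share the assumption, but their bias was not computed. Attenuation is the likelier harm. This warrants an added sensitivity analysis, not a different primary model.

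**What to change.** Keep the single-indicator model as primary. Add to Section 12.5, for both co-primary outcomes, a pre-specified sensitivity version of model (1) in which indicators for period since activation replace I_ij. Report the effect by period and the time-averaged effect, with the averaging weights (equal or by patients) fixed in advance. Present these beside the primary estimate whatever they show. Do not make the primary conclusion depend on a test of constancy, because that would let the data choose the estimand.

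No new data are needed: activation and surgery dates are known. The cost is one extra model per outcome and lower precision for the time-averaged effect. With categorical time and 864 patients per cell, its SE is 0.0172 against 0.0106 with equal weights, a ratio of about 1.6. With patient weights it is 0.0142 to 0.0147, a ratio of 1.34 to 1.38 depending on the wave split. Scaling the stated 0.048 to 0.055 SD:
- Equal weights, ratio 1.60 to 1.62: about 0.077 to 0.089 SD.
- Patient weights, ratio 1.34 to 1.38: about 0.064 to 0.076 SD.

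The text should say that this analysis is less precise, so that a wide interval is not read as evidence against an effect.
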